12.1 Study Design/Endpoints

The principal aim of this pilot study is to examine if exposure to meaningful social rewards during psychotherapy, engages reward circuitry and improves mid- and late-life major depression. The “reward exposure” of this study will consist of meaningful social activities with significant others (“Engage & Connect”). The study will be a pilot RCT that will compare 9-week “Engage & Connect” vs. a Symptom Review and Psychoeducation condition (SRP) for adults older than 50 years with major depression and test the following hypotheses:

During the 9 week course of “Engage & Connect” treatment there will be an:

- H1.** Increase in rsFC of the PVS.
- H2.** Increase in behavioral activation (BADS scale)
- H3.** Reduction in depression severity (MADRS scale).

SH. In “Engage & Connect” treated participants, change in: **SH1a)** rsFC of the PVS and **SH1b)** behavioral activation (BADS) will predict subsequent reduction in depression severity (MADRS). These relationships will not be observed in the SRP treated group. The rationale of this hypotheses is based on the theory that the “Engage & Connect” mechanism of action is reconditioning the PVS, while SRP relies on non-specific mechanisms of action.

To further investigate the PVS correlates of social reward, we developed a social reward fMRI paradigm, modeled after a monetary incentive delay task⁴⁴ and plan to use it in analyses for hypothesis generation.

Analysis Plan

H1, H2, H3: During the 9-week course of “Engage & Connect” there will be an:

- H1.** Increase in rsFC of the PVS
- H2.** Increase in behavioral activation (BADS)
- H3.** Reduction in depression severity (MADRS).

We will implement mixed-effects models using the *lme4* package in R.⁴⁶ For **H1, H2, and H3** we will include subject-specific random intercept and fixed effects for time-related parameter(s). For **SH**, We will estimate a separate mixed-effects model for each of the four a-priori PVS ROIs. Models of PVS ROIs will include change from baseline to Week 5, Week 5 to 9 and models of behavioral activation (BADS scale) and depression severity (MADRS scale) and will include change from baseline to Week 3 to Week 5 and Week 5 to Week 9 as independent variables. Dependent variables will be depression severity at Weeks 5 and Week 9 for PVS ROI models and at Weeks 3, 5, and 9 for BADS model. We will include fixed effects for age, gender, antidepressant use, or any other variable that will be unbalanced between the groups. We will explore in all models the inclusion of higher order(s) of the time variable (e.g., quadratic, cubic, etc.) and choose the final model based on Bayesian Information Criterion (BIC).⁴⁷ We will control the overall Type I error rate at 5% using Holm’s stepdown procedure to adjust for four post-hoc multiple comparisons (four PVS ROIs) in **H1** and five comparisons (four PVS ROIs and BADS) in **SH**.

SH. In “Engage & Connect” treated participants, change in: **SH1a.** rsFC of the PVS; and **SH1b.**

Behavioral activation (BADS) will predict subsequent reduction in depression severity (MADRS). These relationships will not be observed in the SRP treated group. Five mixed-effects models (as described above) will investigate whether change in the predictor is associated with subsequent change in depression severity (MADRS).

Power Analysis

Our primary outcome is change over 9 weeks of “Engage & Connect” in resting state functional connectivity (rsFC) of the Positive Valence System (PVS) (**H1**). Our secondary outcome measures are change in behavioral activation measured by the Behavioral Activation for Depression Scale (BADS) (**H2**); and depression severity, measured by the Montgomery-Asberg Depression Rating Scale (MADRS) (**H3**). Our secondary hypothesis (**SH**) investigates whether early change in the predictors (i.e. rsFC of the PVS and BADS change) predict subsequent change in depression severity (MADRS). We will measure rsFC at baseline, Week 5, and Week 9 and behavioral activation and depression severity at baseline, Week 3, Week 5, and Week 9.

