1.2.3 Exploratory Objectives

Evaluate whether in “Engage & Connect” treated participants, change in rsFC of the PVS and behavioral activation (BADS) predicts subsequent reduction in depression severity (MADRS).

Investigate changes in social reward processing over the course of psychotherapy using a novel Social Incentive Delay (SID) fMRI task

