1.2.5 Secondary Endpoints

Change in BADS scores and MADRS scores over 9 weeks.

2. Background

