12.4 Analysis of Endpoints

12.4.1 Analysis of Primary Endpoints

We will implement mixed-effects models using the *lme4* package in R.⁴⁶ For **H1**, **H2**, and **H3** we will include subject-specific random intercept and fixed effects for time-related parameter(s).

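### The promised overall 5% Type I error is not delivered across H1, H2, H3 and SH (18.5% if independent, at most 20%), and the random-intercept model for H1-H3 may understate the standard error of change

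*Combined protocol and SAP*

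**What the plan says.** **Error rate.** The Analysis Plan in Section 12.1, repeated in Section 12.4.2, promises "We will control the overall Type I error rate at 5" per cent. It then applies Holm's procedure to four ROI comparisons in H1 and, as a separate set, to "five comparisons (four PVS ROIs and BADS") in SH. No adjustment or significance level is given for H2 (BADS) or H3 (MADRS). There is no testing order, gatekeeping or alpha split.

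**Labels.** Section 12.4.1, headed "Analysis of Primary Endpoints", covers H1, H2 and H3 together. Section 1.2.5 lists as secondary "Change in BADS scores and MADRS scores over 9 weeks", and the Power Analysis in Section 12.1 agrees: "Our secondary outcome measures are change in behavioral activation measured by the Behavioral Activation for Depression Scale (BADS"), with MADRS named next. The same paragraph introduces SH as "Our secondary hypothesis", and Section 12.4.2 places SH under secondary endpoints. The synopsis and Section 1.2.3 list that question as exploratory, namely whether "change in rsFC of the PVS and behavioral activation (BADS) predicts subsequent reduction in depression severity (MADRS").

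**Model.** For H1-H3, Sections 12.1 and 12.4.1 say "we will include subject-specific random intercept and fixed effects for time-related parameter(s"). No random slope is named. The order of the time term is chosen by BIC. rsFC is measured at weeks 0, 5 and 9; BADS and MADRS at weeks 0, 3, 5 and 9.

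**The concern.** Holm holds the error rate at 5% inside the set of tests it is given. Two separate Holm sets plus two unadjusted tests do not add up to an overall 5%, so the plan claims a property it does not have. The label conflict makes this worse: a reader who follows the heading of Section 12.4.1 would take three separately tested outcomes as primary.

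The second issue concerns the p-values that go into Holm. A random-intercept model assumes one common slope and constant within-person correlation. If people truly change by different amounts, the model treats between-person variation in change as visit-level noise and averages it over too many degrees of freedom, so the standard error of the mean slope is too small. The plan itself expects such differences, since SH needs participants to vary in how much they change. This touches H1, the one hypothesis whose 5% Holm was meant to protect. No such effect is claimed for SH.

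Third, if BIC picks the order of time, the parameter that tests H1 is not known in advance.

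**Working it through.** **1. The plan's own 5%.** H1: Holm's first step is 0.05/4 = 0.0125, and 4 × 0.0125 = 0.05. SH: first step 0.05/5 = 0.01, and 5 × 0.01 = 0.05. Both reproduce 5% as separate families.

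**2. Across families.** Assumptions: H2 and H3 are each tested at 5% (the documents give no level), all nulls are true, and every test keeps its nominal level. With independent families:

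- H1, H2, H3 and SH: 1 − 0.95⁴ = 18.5%; upper bound 4 × 5% = 20%.
- H1-H3 only (the set under Section 12.4.1): 1 − 0.95³ = 14.3%; upper bound 15%.
- H1 and SH only (the two sets the sentence names): 1 − 0.95² = 9.75%; upper bound 10%.

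The tests share participants, so independence is an illustration. Simulating 11 equally correlated two-sided z statistics (4 ROIs, BADS, MADRS, 5 in SH), with Holm within H1 and within SH:

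| Common correlation | H1-H3 and SH | H1-H3 | H1 and SH | One Holm over six tests (4 ROIs, BADS, MADRS) |
|---|---|---|---|---|
| 0 | 18.4% | 14.2% | 9.6% | 4.9% |
| 0.3 | 16.5% | 13.2% | 8.7% | 4.6% |
| 0.5 | 13.9% | 11.8% | 7.4% | 4.2% |
| 0.8 | 9.1% | 8.6% | 4.5% | 2.8% |

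The first row lies slightly below the closed forms because Holm over independent tests is itself a little under 5% (4.9%).

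**3. Random intercept without random slope.** Let r = SD of participants' true 9-week change / residual SD. The documents give no variance components, so r is an assumption and a range is shown. For a linear time term and complete visits:

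- Sxx = sum of squared deviations of the visit weeks: 40.67 for weeks 0, 5, 9 and 42.75 for weeks 0, 3, 5, 9.
- Share of individual-slope variance that is true: s = q/(1 + q), with q = (r/9)² × Sxx.
- True variance / model variance of the mean slope = 1/[(1 − s) + s/(T − 1)], with T visits.
- Actual two-sided error at nominal 5% = 2 × [1 − Φ(1.96/√ratio)].

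Example, rsFC at r = 1: q = 40.67/81 = 0.502; s = 0.334; ratio = 1/(0.666 + 0.167) = 1.20; the model SE is 1/√1.20 = 0.91 of the true SE; error 7.4%.

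| r | rsFC: SE too small by | rsFC: error | BADS/MADRS: SE too small by | BADS/MADRS: error |
|---|---|---|---|---|
| 0 | 0% | 5.0% | 0% | 5.0% |
| 0.5 | 3% | 5.7% | 4% | 6.0% |
| 1.0 | 9% | 7.4% | 12% | 8.6% |
| 1.5 | 14% | 9.3% | 20% | 11.7% |

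**4. Effect on the H1 Holm family.** At s = 0.5 (r about 1.4) the rsFC ratio is 1.333. Holm's first critical value is 2.498, so each ROI is rejected with probability 2 × [1 − Φ(2.498/√1.333)] = 3.05%. With four independent ROIs the family error is 1 − (1 − 0.0305)⁴ = 11.7%; with ROI correlation 0.5 it is 9.9% by simulation. The stated level is 5%.

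**5. Simulation check.** With 20,000 replicates and n = 30 or n = 27 (10% attrition), the random-intercept test at s = 0.5 rejected 9.0-9.5% for rsFC and 11.1% for BADS/MADRS. The closed forms give 9.0% and 11.0%. At s = 0 it rejected 4.9-5.2%. A test on participants' own slopes and a baseline-to-Week-9 contrast both stayed at 4.7-5.4% in every scenario.

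**The case against.** The strongest reply is that the sentence, read to its end, names only H1 and SH and may simply mean 5% within each. On that reading both families are as stated, and the 18.5% measures a claim the authors did not intend. Even across those two families the rate is at most 10%, and 4.5% at correlation 0.8. H1 is the only primary outcome in the synopsis, Section 1.2.4 and the Power Analysis, and leaving secondary outcomes unadjusted in a 60-person pilot is defensible. If the H2 and H3 nulls are false, as the background on Engage suggests, only H1 and SH can contribute false positives.

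Much of this stands. It argues for leaving H2 and H3 unadjusted, not for the word overall. If 5% within each family is meant, the sentence is wrong as written and one line corrects it.

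On the model, it can fairly be said that r is unknown, that there is no inflation at r = 0, and that the plan does not say the random intercept is the only random effect. Section 10.1 also mentions slopes of MADRS change within a mixed model. That section specifies no random slope and concerns MADRS only. The figures assume a linear time term, complete visits and two-sided tests, so they show direction and plausible range. The simulations covered the subject-slope test and the Week-9 contrast, not every software fit recommended below, and treated attrition as a smaller sample.

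**Conclusion.** The concern holds. The documents do not support an overall 5% Type I error. The rate over H1, H2, H3 and SH is 18.5% with independent families, at most 20%, and 9.1% even with all tests correlated at 0.8, given H2 and H3 at 5% each and all nulls true. H1 alone is controlled at 5%, provided its p-values are valid. The conflicting labels for BADS, MADRS and SH are plain in the text.

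The standard-error point is conditional. There is no inflation if slopes are equal and correlation is constant. For r between 0.5 and 1.5 a nominal 5% becomes 5.7% to 9.3% for rsFC and 6.0% to 11.7% for BADS and MADRS. If that happens, the 20% bound no longer applies either. No error-rate figure is attached to the BIC choice; the defect there is that the test of H1 is not fixed beforehand.

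These points should be corrected before analysis. They do not call the design into question.

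**What to change.** 1. **Restate the claim.** For example: Type I error is controlled at 5% across the four ROIs of H1 by Holm; H2 and H3 are secondary and unadjusted; SH is exploratory, with Holm within its five tests; no overall 5% claim is made. If control over H1-H3 is wanted, run one Holm procedure over the six tests (four ROIs, BADS, MADRS), with first step 0.05/6 = 0.0083.
2. **Align the labels.** Bring the headings of Sections 12.4.1 and 12.4.2 and the Power Analysis text into line with Section 1.2.
3. **Let participants differ in change.** For H1-H3 use categorical visit with unstructured within-subject covariance (gls or mmrm in R), or add a subject random slope in lme4, with Satterthwaite or Kenward-Roger degrees of freedom.
4. **Fix the test.** Prespecify the baseline-to-Week-9 contrast for H1-H3, which matches endpoints already defined as change over 9 weeks, in place of a BIC-selected time term.

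The cost is SAP wording and a different model call, with no new data or participants. The downside is slightly wider intervals, more variance parameters (unstructured covariance has 6 for three visits and 10 for four, against 2 for a random intercept), and a less favourable error-rate statement.

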12.2 Sample Size/Accrual Rate

The annual participant recruitment plan is as follows: 11 participants in Year 1 (5 SRP, 6 “Engage & Connect”), 14 in Year 2 (7 per group), 17 in Year 3 (9 SRP, 8 “Engage & Connect”), and 18 in Year 4 (9 per group). MRI scans and clinical assessments at Weeks 5 and 9 for 10 participants will be completed in the first four months of Year 5. Statistical analyses will be conducted in Year 6 and Year 7.

12.3 Stratification Factors

The sample will be stratified by age so that 50% of participants recruited are between ages 65-85 and 50% are between ages 50-65. The stratification is aimed to allow investigation of the research questions in a balanced sample of middle-aged and older adults with major depression.

12.4 Analysis of Endpoints

12.4.1 Analysis of Primary Endpoints

We will implement mixed-effects models using the *lme4* package in R.⁴⁶ For **H1**, **H2**, and **H3** we will include subject-specific random intercept and fixed effects for time-related parameter(s).

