2.3 Rationale

The proposed study will be the first study to test target engagement of “Engage & Connect”, a social reward-focused intervention for mid- and late-life depression. “Engage & Connect” is innovative because: 1) It is directly informed by neurobiological research and designed to address dysfunction of PVS, a core component of depression; 2) It is based on data

demonstrating that exposure to social rewards has the highest probability to improve depressive symptoms; 3) It is streamlined so that it can potentially be used by community clinicians. The NIMH Strategies 3.1; 3.2 encourage the development of novel streamlined treatments informed by advances in neuroscience.

To our knowledge, the proposed study will be the first to examine neural processing of social rewards in mid- and late-life depression. It is based on computational modeling, which identified perceived social support as the strongest predictor of early response to psychotherapy and examines whether PVS changes by mid-treatment predict response of depression to “Engage & Connect”. Along with other PVS function measures, it uses a novel social reward fMRI paradigm to examine PVS change and its relationship to “Engage & Connect” response. Behavioral tasks and clinical scales across multiple units of analysis are quick, cost-effective, and easy to administer, making them feasible to use in future large-scale studies and as screening tools in clinical settings.

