“Engage” targets the PVS system using ‘reward exposure’ intervention – engagement in rewarding activities implemented in weekly ‘action plans’ developed by the depressed patient and the therapist.²² In patients with negativity bias, apathy, or inadequate emotional regulation, therapists provide targeted interventions so that reward exposure proceeds unimpeded. “Engage & Connect”, a modified adapted version of “Engage”, focuses on exposure to rewarding activities with significant others. During sessions, the therapist and patient will select a social activity (i.e. interaction with a significant other) and formulate a stepped plan to complete this goal. By week 3, therapists will assess patients’ barriers to reward exposure – negativity bias, apathy, inadequate emotion regulation, as well as interpersonal conflicts and social skills deficits, which may hinder social interactions – and address barriers through targeted strategies.

Symptom Review and Psychoeducation (SRP)

SRP is a comparison condition that resembles what a good clinician does in evaluating, reassuring, and educating a depressed patient. Each session begins with reviewing the depressed patient’s symptoms, then assessing patient’s knowledge base about depression. Identifying patient’s misconceptions about depression will guide the selection of educational material to be presented in each session. Comprehending depression-related information is contaminated by pessimism, denial, misconceptions, and stigma. The role of SRP therapist is to impart valuable information, despite these complexities. Conveying information is a process. The SRP therapist needs to be aware of “where the patient” is and offer information for which he/she has readiness to accept. SRP therapists do not engage in other interventions. Arguably, SRP is a condition with: 1) non-specific active therapeutic ingredients; 2) little overlap with the therapeutic ingredients of “Engage & Connect”; and 3) exposure of patients to therapists equal to that of “Engage & Connect”. We used a similar comparison condition in a recently completed psychotherapy study of post-stroke depression and found that SRP leads to reduction in depression severity (R01 MH096685, PI: [name]).

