10.1 Response Criteria

Reduction in depression severity over the course of 9 weeks of treatment (slopes of change in MADRS scores will be calculated within mixed-effects model approach, see Statistical Analysis).

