12.4.2 Analysis of Secondary Endpoints

For **SH**, We will estimate a separate mixed-effects model for each of the four a-priori PVS ROIs. Models of PVS ROIs will include change from baseline to Week 5, Week 5 to 9 and models of behavioral activation (BADS scale) and depression severity (MADRS scale) and will include change from baseline to Week 3 to Week 5 and Week 5 to Week 9 as independent variables. Dependent variables will be depression severity at Weeks 5 and Week 9 for PVS ROI models and at Weeks 3, 5, and 9 for BADS model. We will include fixed effects for age, gender, antidepressant use, or any other variable that will be unbalanced between the groups. We will explore in all models the inclusion of higher order(s) of the time variable (e.g., quadratic, cubic, etc.) and choose the final model based on Bayesian Information Criterion (BIC).⁴⁷ We will control the overall Type I error

rate at 5% using Holm's stepdown procedure to adjust for four post-hoc multiple comparisons (four PVS ROIs) in **H1** and five comparisons (four PVS ROIs and BADS) in **SH**.

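### The H1–H3 models, including the primary rsFC analysis, contain no between-arm test, so as written the trial does not compare Engage & Connect with SRP

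*Combined protocol and SAP*

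**What the plan says.** **Design.** Section 12.1 states: "The study will be a pilot RCT that will compare 9-week" Engage & Connect with SRP. The synopsis and Sections 1.2.1 and 3.1 say the same, and the objectives ask what Engage & Connect leads to.

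**Hypotheses.** H1–H3 (Sections 3.1 and 12.1) are worded as changes during the Engage & Connect course. The Power Analysis text in Section 12.1 follows suit: "Our primary outcome is change over 9 weeks of" Engage & Connect, in rsFC of the PVS.

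**Models.** For H1–H3, Sections 12.1 and 12.4.1 say "we will include subject-specific random intercept and fixed effects for time-related parameter(s"). Section 12.4.2 adds age, gender, antidepressant use, "or any other variable that will be unbalanced between the groups", and higher-order time terms chosen by BIC. Section 10.1 says of MADRS that "slopes of change in MADRS scores will be calculated within mixed-effects model approach". Holm's procedure covers four ROIs in H1 and five comparisons in SH.

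**Role of SRP.** Among the hypotheses, SRP appears explicitly only in SH: "These relationships will not be observed in the SRP treated group".

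**The concern.** A time effect answers whether the outcome moved over 9 weeks. It does not answer whether it moved more under Engage & Connect than under SRP, which is what the randomised comparator is there to show. Section 7.1 presents SRP as matching therapist exposure with little overlap in active ingredients; the H1–H3 models do not use that control.

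The practical risk is that a significant time term is reported as an effect of Engage & Connect when SRP changed just as much. For MADRS, shared improvement is plausible. Entry requires a score of at least 20 (Section 4.2), so regression to the mean is likely, and Section 7.1 reports using a "similar comparison condition in a recently completed psychotherapy study of post-stroke depression and found that SRP leads to reduction in depression severity". That was a different population, since history of stroke is excluded here (Section 4.3). For rsFC the documents neither support nor rule out a shared change. The point there is that the specified test could not detect one.

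**Working it through.** **1. Is there a contrast anywhere?** I looked in each place where one could sit.

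| Place | Content | Arm contrast for H1–H3? |
|---|---|---|
| Sections 3.1, 12.1 (hypotheses) | Change during Engage & Connect | No |
| Section 12.1 (primary outcome) | Change over 9 weeks of Engage & Connect | No |
| Sections 12.1, 12.4.1 (model) | Random intercept, time terms | No |
| Sections 12.1, 12.4.2 (covariates) | Age, gender, antidepressant use, unbalanced variables | No |
| Section 12.4.2 (BIC, Holm) | Time order; four ROIs, five SH comparisons | No |
| Section 10.1 | MADRS slopes | No |
| Section 12.6.2 | All included subjects evaluated for response | No |

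**2. Inputs.** The yearly accrual in Section 12.2 reproduces the sample size: 11 + 14 + 17 + 18 = 60, with SRP 5 + 7 + 9 + 9 = 30 and Engage & Connect 6 + 7 + 8 + 9 = 30. Attrition of about 10% (Sections 4.1 and 7.12) leaves 30 × 0.9 = 27 completers per arm, 54 in all. The overall alpha is 5%; Holm's first step over four ROIs is 0.05/4 = 0.0125. The text headed Power Analysis gives no effect size, SD or power, so there is no stated power to reproduce. My assumptions are two-sided tests and changes of 0.3, 0.5 and 0.8 in units of the SD of the baseline-to-Week-9 change.

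**3. Time test when both arms change equally.** This is a one-sample noncentral t with noncentrality d√n and n − 1 degrees of freedom. For d = 0.5 the noncentrality is 0.5 × √27 = 2.60 for one arm and 0.5 × √54 = 3.67 for both.

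| Shared change (SD) | One arm, n = 27, 0.05 | One arm, 0.0125 | Both arms, n = 54, 0.05 | Both arms, 0.0125 |
|---|---|---|---|---|
| 0.3 | 32% | 15% | 58% | 36% |
| 0.5 | 71% | 48% | 95% | 86% |
| 0.8 | 98% | 92% | >99% | >99% |

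These figures are power to detect change over time. They become false conclusions only if read as an effect over SRP.

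A simulation at alpha 0.05 (random-intercept model, linear time, visits at Weeks 0, 5 and 9, correlation 0.5, 20,000 runs) gives 34%, 73% and 98% for one arm and 59%, 96% and 100% pooled. A baseline-adjusted between-arm test in the same scenarios rejects in 5.1%, 4.9% and 5.1% of runs (1.2–1.4% at 0.0125).

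**4. Pooled model, change in SRP only.** With 0 in Engage & Connect and 0.5 SD in SRP, the pooled mean change is 0.25 SD. The pooled time test is significant in about 44% of simulated trials (24% at 0.0125).

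**5. What a between-arm test can detect.** This is a two-sample t with noncentrality d√(27/2) and 52 degrees of freedom. Baseline adjustment multiplies the SD of the change by √((1 + r)/2), with 51 degrees of freedom, where r is the baseline–Week 9 correlation, assumed 0.3–0.7 (factor 0.81–0.92).

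| Test | Detectable at 80% power, 0.05 | 0.0125 | Power at 0.5 SD, 0.05 | 0.0125 |
|---|---|---|---|---|
| Within-arm, n = 27 | 0.56 SD | 0.68 SD | 71% | 48% |
| Between-arm, change score | 0.78 SD | 0.94 SD | 44% | 24% |
| Between-arm, baseline-adjusted | 0.63–0.72 SD | 0.76–0.87 SD | 50–61% | 29–39% |

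**The case against.** The strongest reply is that the model fits the hypotheses as worded. H1–H3 speak of change during Engage & Connect, Section 2.3 says "The proposed study will be the first study to test target engagement of" this therapy, and the trial calls itself a pilot. A within-arm time effect is a legitimate answer to a within-arm target-engagement question. That stands as a possible intention, but the plan never says that no comparison is meant, and it repeatedly says the opposite.

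A second reply is that the arm term is implied, because adjusting for imbalance between groups makes sense mainly if both arms are modelled. That suggests two-arm models, but covariate adjustment does not create a treatment contrast; a pooled model without an arm term averages the two treatments.

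Third, Section 12.6.2 says all included subjects will be evaluated for response, and Sections 7.10 and 8.1 invite participants who discontinue to continue assessments. This helps a little, but it does not say which arm or arms enter the H1–H3 models. Section 8.2 also allows withdrawn randomised participants to be replaced, which leaves the analysis set open.

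Finally, the percentages rest on assumed effect sizes and on completers, whereas a mixed model can use partial data, and a slope contrast would be as valid as a Week 9 contrast. All true: the percentages are illustrations, and the omission does not depend on them.

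**Conclusion.** The concern holds and must be fixed, because it affects the primary analysis of a randomised trial. Followed as written, the H1–H3 models cannot distinguish an effect of Engage & Connect from change shared with SRP. Leaving the arms and the contrast open also lets them be chosen after the data are seen.

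The absence of a contrast is a matter of text and rests on no assumption. The size of the risk does: it depends on how much SRP participants change, which the documents make plausible for MADRS and leave unknown for rsFC.

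**What to change.** Choose one of two courses before any outcome data are analysed.

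**(a) Make H1–H3 comparative.** Restate them as greater change in Engage & Connect than in SRP. Fit all randomised participants as assigned, keeping any who are replaced, with visit and arm-by-visit terms and a common baseline mean. Make the arm difference at Week 9 the test, apply Holm across the four ROIs for H1, and report within-arm change descriptively. An arm-by-time slope contrast is an acceptable alternative if fixed in advance. State the between-arm detectable effects given above.

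**(b) Keep H1–H3 within-arm.** Say so, name the arm or arms in each model, and state that no comparative or efficacy conclusion will be drawn from them.

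**Cost.** Neither course needs new data. Course (a) changes the primary hypothesis and exposes low power. By t-test at 0.05, 80% power for a 0.5 SD difference needs 64 completers per arm, 128 in all, or 128/0.9 = 142.2, about 143 randomised, against 60 planned. Course (b) costs only wording but gives up the comparative claim.

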| Study Description: | 
Major depression in mid- and late-life is characterized with abnormalities in the Positive Valence System (PVS). Exposure to rewarding experiences can target these abnormalities and in turn, reduce depression severity. Given the high prevalence of loneliness and social isolation in late life, socially rewarding interactions are especially important. Engagement in social interactions with significant others during reward-based psychotherapy reduces depression and increases behavioral activation. The aim of the study is to examine if exposure to meaningful social rewards during psychotherapy, engages PVS circuitry and improves mid- and late-life major depression. The "reward exposure" of this study will consist of meaningful social activities with significant others ("Engage & Connect"). The study will be a pilot RCT that will compare 9-week "Engage & Connect" vs. a Symptom Review and Psychoeducation condition (SRP) for adults older than 50 years with major depression. We will investigate changes in resting-state functional connectivity, social reward processing during an fMRI-based social reward task, and changes in behavioral outcomes over the course of treatment.
 |
| Sample Size: | N= 60 |
| Enrollment: | This study will enroll 60 subjects and screen up to 90 subjects. |
| Study Population: | Individuals aged 50-85 with major depression |
| Enrollment Period: | The study will recruit participants over 5 years |
| Study Design: | 
This is a randomized controlled trial comparing two psychosocial interventions. We will assess target engagement of the PVS through functional connectivity at rest (rsFC), a self-report measure of behavioral activation (BADS), and performance on a novel fMRI social reward paradigm, during two psychotherapies for middle-aged and older adults with major depression, i.e., "Engage & Connect" therapy (n = 30) and a comparison condition of Symptom Review and Psychoeducation (SRP; n = 30). Participants will receive nine weekly therapy sessions. We will administer research assessments at baseline, Weeks 3, 5, and 9 and MRI scans at baseline, Week 5 and 9. All participants will provide informed consent prior to enrolling in the study.
 |
| Description of Sites/ Facilities Enrolling | |

| | |
|----------------------------------|---|

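### The H1–H3 models pre-specify neither an arm contrast nor use of the outcome's own baseline; baseline adjustment could cut the variance of a standard Week 9 comparison with SRP by 15–35%, for an assumed correlation of 0.7–0.3 and equal variances

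*Combined protocol and SAP*

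**What the plan says.** Section 12.1 describes the design as randomised and comparative: "The study will be a pilot RCT that will compare 9-week" Engage & Connect with SRP. The synopsis gives 30 participants to Engage & Connect and 30 to "a comparison condition of Symptom Review and Psychoeducation (SRP; n = 30".

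On timing, 12.1 says: "We will measure rsFC at baseline, Week 5, and Week 9 and behavioral activation and depression severity at baseline", with BADS and MADRS repeated at Weeks 3, 5 and 9. All three outcomes therefore have a pre-treatment value.

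The whole model for H1–H3, in 12.1 and again in 12.4.1, is: "we will include subject-specific random intercept and fixed effects for time-related parameter(s". For MADRS, 10.1 adds that "slopes of change in MADRS scores will be calculated within mixed-effects model approach", so baseline is most naturally read as one of the outcome visits, though the plan never says this outright. No arm term or arm-by-time term is named. The primary outcome is worded as change within one arm: "Our primary outcome is change over 9 weeks of" Engage & Connect.

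The covariate rule, in 12.1 and 12.4.2, is: "We will include fixed effects for age, gender, antidepressant use, or any other variable that will be unbalanced between the groups". It follows the description of the SH models, and whether it reaches H1–H3 is unclear. The outcome's own baseline is not on the list.

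**The concern.** Randomisation makes the true baseline means of the two arms equal. A comparison that uses this fact, by taking the baseline value as a covariate or by giving both arms one baseline mean, is usually more precise than a comparison of raw changes. It also handles chance baseline differences properly, where raw change over-corrects for them. The plan commits to neither.

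The gap matters because the H1–H3 model must be extended before it can compare the arms at all. The habitual extension adds arm, time and arm-by-time, which leaves the arm means free at baseline and estimates a difference in raw change. With about 27 participants per arm after attrition, and Holm adjustment over four ROIs for H1, precision available from data already collected should not be left to chance.

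**Working it through.** **The plan's own figures.** The documents give no effect size, SD, correlation or power, so N = 60 cannot be re-derived. The accrual plan in 12.2 does sum correctly: 11 + 14 + 17 + 18 = 60. The roughly 10% attrition in 4.1 and 7.12 leaves 30 × 0.9 = 27 per arm.

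**Assumptions, not in the documents.** ρ is the correlation between baseline and Week 9, taken as 0.3 to 0.7. Variances are equal at all visits and the correlation is common, as a random-intercept model implies. Data are complete.

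**Step 1: Week 9 contrast.** Let σ² be the variance at a visit and n the number per arm.
- Arm means free at baseline: variance = 2(1−ρ) × 2σ²/n.
- Baseline as covariate (large samples), or a common baseline mean: variance = (1−ρ²) × 2σ²/n.
- Ratio = (1−ρ²) / [2(1−ρ)] = (1+ρ)/2, so the reduction is (1−ρ)/2.

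The power columns are illustrative: 27 per arm, two-sided 5% before Holm, an assumed Week 9 difference of 0.5 SD, power = Φ(0.5/√(2v/27) − 1.96), where v is the multiplier 2(1−ρ) or (1−ρ²).

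| ρ | 2(1−ρ) | 1−ρ² | Ratio | Reduction | Power, free baseline | Power, adjusted |
|---|---|---|---|---|---|---|
| 0.3 | 1.40 | 0.91 | 0.65 | 35% | 34% | 49% |
| 0.5 | 1.00 | 0.75 | 0.75 | 25% | 45% | 56% |
| 0.7 | 0.60 | 0.51 | 0.85 | 15% | 66% | 73% |

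Outside this range, the reduction is 40% at ρ = 0.2 and 10% at ρ = 0.8.

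**Step 2: linear slope.** Section 10.1 speaks of slopes, so the same comparison was made for a linear arm-by-time term, free baseline against common baseline mean. With m visits at weeks t, the variance ratio is Σ(t−t̄)² / [Σt² − ρ(Σt)²/(1+(m−1)ρ)].
- rsFC, weeks 0, 5, 9: Σt² = 106, (Σt)² = 196, Σ(t−t̄)² = 40.67. Ratios are 40.67/69.25 = 0.587, 40.67/57.00 = 0.713 and 40.67/48.83 = 0.833. Reductions are 41%, 29% and 17% at ρ = 0.3, 0.5 and 0.7.
- BADS and MADRS, weeks 0, 3, 5, 9: Σt² = 115, (Σt)² = 289, Σ(t−t̄)² = 42.75. Ratios are 0.616, 0.747 and 0.859. Reductions are 38%, 25% and 14%.

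**Step 3: unequal variances.** Section 4.2 requires MADRS of at least 20 at entry, which restricts the baseline range. Let k = baseline SD / later SD (assumed; not in the documents). The variance of raw change is then proportional to 1 + k² − 2ρk = (1−ρ²) + (k−ρ)². For baseline as covariate, the ratio (1−ρ²) / [(1−ρ²) + (k−ρ)²] never exceeds 1 in large samples and equals 1 when k = ρ. A common baseline mean fitted with only a random intercept has no such guarantee, because that model forces equal variances. Ratios to the free-baseline variance, three visits:

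| k | Covariate: ρ = 0.3, 0.5, 0.7 | Common mean, random intercept only: ρ = 0.3, 0.5, 0.7 |
|---|---|---|
| 1.0 | 0.65, 0.75, 0.85 | 0.65, 0.75, 0.85 |
| 0.8 | 0.78, 0.89, 0.98 | 0.79, 0.91, 1.02 |
| 0.7 | 0.85, 0.95, 1.00 | 0.86, 0.98, 1.10 |
| 0.6 | 0.91, 0.99, 0.98 | 0.93, 1.05, 1.16 |

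The covariate form gains little or nothing in the lower right of the table, but it does not lose. The common-mean form with a random intercept can lose up to about 16% in this range.

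**The case against.** The strongest reply is that the written model contains no arm term. It produces no comparison with SRP, so there is no variance of that comparison to lose. This is correct. The absent arm-by-time contrast is the more basic gap, and the loss arises only under one way of filling it. Adding arm-by-time without an arm main effect would already give both arms a common baseline mean, and with equal variances nothing would be lost. The documents do not say which form would be used, which is the reason to settle it in the same edit.

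A reader might infer that keeping baseline among the outcome visits is itself the mistake. It is not: a common-baseline-mean model does the same. The cost comes from leaving the arm means free at baseline.

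A reader might also infer that baseline is never adjusted for. The unbalanced-variable clause could admit it. But that clause depends on the observed data, sits in the SH text, and ties adjustment to visible imbalance, whereas the gain in precision does not depend on imbalance.

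Finally, a free-baseline model is valid and unbiased under randomisation, and this is a pilot. That stands. The point concerns precision and pre-specification, not validity.

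**Conclusion.** The point holds in a conditional form. H1–H3 pre-specify no arm-by-time contrast and no use of the outcome's own baseline. If the comparison is built with arm means free at baseline, baseline adjustment would reduce the Week 9 variance by 15–35%, for ρ from 0.7 to 0.3 and equal variances across visits. Both conditions are assumptions. With a smaller baseline SD the gain shrinks, possibly to near zero, and MADRS is the outcome where the entry floor makes this plausible.

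The documents do not support three stronger readings:
- That the plan as written discards a fixed share of variance: there is no written contrast and no stated ρ.
- That using the equal-baseline fact always helps: under a random-intercept covariance it can hurt.
- That rsFC gains most: no rsFC correlation or reliability is given.

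Nor does the failure to re-derive N = 60 show that it is wrong. The change is worth making because it is almost free.

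**What to change.** In 12.4.1, define the target for each rsFC ROI, BADS and MADRS as the Week 9 difference, Engage & Connect minus SRP. Estimate it from a mixed model of the post-baseline visits with arm, visit, arm-by-visit, baseline value and baseline-by-visit as fixed effects. State this in advance, independently of the unbalanced-variable clause.

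A model with all visits as outcomes and a common baseline mean is an acceptable alternative only with an unstructured covariance (variances and correlations free by visit). The two approaches should not be combined.

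The cost is SAP wording, changed model code, and one baseline slope per post-baseline visit: two parameters for rsFC, three for BADS and MADRS. Estimating the baseline slope inflates the variance by roughly 2% at this sample size. No new participants, visits or scans are needed.
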